Secondary Objectives	
To assess the effect of serelaxin as add-on therapy to SOC versus SOC alone in reducing in-hospital WHF requiring rescue therapy or all-cause death or readmission for heart failure, from randomization through Day 14.
 
To assess the effect of serelaxin as add-on therapy to SOC versus SOC alone in reducing the number of patients with persistent signs or symptoms of HF / not showing an improvement versus baseline conditions from randomization through Day 5 (persisting need of IV therapy for HF).
 
To evaluate the effect of serelaxin as add-on therapy to SOC versus SOC alone in reducing the rate of renal deterioration (defined as ≥ 0.3 mg/dL increase in serum creatinine), from randomization through Day 5.
 
To evaluate the effect of serelaxin as add-on therapy to SOC versus SOC alone in modifying the index length of hospital stay (LOS) by location (e.g., ICU, CCU, cardiology department) in days (and hours for ICU).
 
To evaluate the safety and tolerability of intravenous serelaxin in AHF patients during a period of 30 days following exposure.
 
To collect data on health-related quality of life (HRQoL) and economic burden to provide a more comprehensive analysis of the burden of HF, beyond the clinical outcomes.

Study design	This is a multicenter, prospective, open-label, randomized study.

Population	The study population will consist of male and female patients (≥ 18 years old) admitted to the hospital for AHF, with systolic BP ≥ 125 mmHg and mild-to-moderate renal impairment.

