2.2 Secondary objectives

The secondary objectives of the study are the following:

- To assess the effect of serelaxin as add-on therapy to SOC versus SOC alone in reducing in-hospital WHF requiring rescue therapy or all-cause death or readmission for heart failure, from randomization through Day 14.
- To assess the effect of serelaxin as add-on therapy to SOC versus SOC alone in reducing the number of patients with persistent symptoms or signs of HF / not showing an improvement versus baseline conditions from randomization through Day 5 (persisting need of IV therapy for HF).
- To evaluate the effect of serelaxin as add-on therapy to SOC versus SOC alone in reducing the rate of renal deterioration (defined as ≥ 0.3 mg/dL increase in serum creatinine), from randomization through Day 5.
- To evaluate the effect of serelaxin as add-on therapy to SOC versus SOC alone in modifying the index length of stay (LOS) by location (e.g., ICU, CCU, cardiology department) in days and hours (ICU).
- To evaluate the safety and tolerability of intravenous serelaxin in AHF patients during a period of 30 days following exposure.
- To collect data on health-related quality of life (HRQoL) and economic burden to provide a more comprehensive analysis of the burden of HF, beyond the clinical outcomes.

3 Investigational plan

[figure not shown]

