3.6 Risks and benefits

The management of AHF remains an area of unmet medical need, even though, therapies are available to improve AHF-related symptoms, no evidence based therapy for the treatment of AHF is currently available.

Previous studies with serelaxin ([Teerlink et al., 2011 and 2013](#)) showed significant improvement in dyspnea and signs and symptoms of congestion, and demonstrated an association of the drug with significant reductions in early worsening heart failure events and length of stay during the index hospitalization, including duration of intensive care. Moreover, pre-specified biomarker changes in previous studies suggest serelaxin therapy has a protective effect on both the heart and kidney.

Serelaxin was generally well tolerated with no notable differences in the overall adverse event profile compared to placebo. Although a decrease in blood pressure can occur due to the vascular mechanism of action of the drug, worse outcomes were not observed. In order to ensure patient safety, the protocol provides instructions for the management of systolic blood pressure (SBP), including close and careful monitoring as well as mandatory dose adjustment or stopping rules.

The risk to subjects in this trial will be minimized by compliance with the eligibility criteria and close clinical monitoring. Since the potential of immunogenicity as a result of repeated intravenous dosing has not yet been fully characterized, those patients who participated in prior serelaxin clinical studies will be excluded. It is also important to note that all patients in

this study will be required to receive standard of care background HF management during hospitalization as well as the period of 30 days following exposure.

Refer to the Investigator's Brochure (IB) for additional information regarding the safety profile of serelaxin.

4 Population

Similarly to the RELAX-AHF study, subjects will be selected among patients who have been admitted with AHF, who have normal to elevated blood pressure (SBP \geq 125 mmHg at the start and at the end of the screening period) and have impaired renal function defined as an eGFR \geq 25 and \leq 75 ml/min/1.73m² at screening (calculated using the sMDRD equation).

The study plans to randomize approximately 3183 patients in approximately 600 study centers mainly in Europe.

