6.4.3 Index Length of hospital stay

Changes in index length of hospital stay and per location (emergency ward, emergency care unit, etc.) will be evaluated by treatment group.

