Renal deterioration will be assessed as the proportion of patients with an increase of ≥ 0.3 mg/dL from screening in serum creatinine levels. Absolute frequencies and proportions of patients with renal deterioration at each day until Day 5, at discharge and at Day 14 in each treatment group will be provided, together with standard errors, asymptotic (Wald) and exact (Clopper-Pearson) confidence limits. The rate of renal deterioration in the two groups will be compared by means of Chi square test at each time point. In case of cell frequencies less than 5, Fisher Exact test will be used.

Index length of hospital stay

Index length of hospital stay (in hours) will be defined as the index discharge date and time minus the index hospitalization start date and time.

Subjects still in the hospital at Day 30 will be censored at the end of Day 30. Subjects who die during the initial hospitalization will be assigned the maximum length of stay (including those censored at Day 30) plus 24 hours. Treatment groups will be compared using a Wilcoxon rank-sum test. Descriptive statistics by treatment group will be presented. Analysis will be done overall and by location (e.g. ICU, CCU, cardiology department).

Death through Day 30

The time (in days) from randomization to the event will be used for analysis. Subjects without an event will be censored at the earlier of the last contact date or Day 30. Treatment groups will be compared using a generalized Wilcoxon test. The Kaplan-Meier estimates of the survival functions for each treatment group will be plotted.

Re-hospitalization post-discharge

The number of re-hospitalizations per patients by treatment group will be described. Treatment groups will be compared using a Wilcoxon rank-sum test. The number of patients with 1, 2, ≥ 2 re-hospitalization will be summarized and treatment groups will be compared with a Chi-Square test. In case of cell frequencies less than 5, Fisher Exact test will be used.

Time to first re-hospitalization (in days) will be defined as the re-hospitalization date minus the randomization date. Subjects still in hospital at Day 30 will be censored at Day 30. Subjects who die when not hospitalized will be assigned as the date of death as their time to re-hospitalization. Treatment groups will be compared using a generalized Wilcoxon test. The Kaplan-Meier estimates for each treatment group will be plotted. Descriptive statistics by treatment group will be presented.

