fibrillation in medical history (“Occurrence” is marked “Yes” on the “Medical History – Protocol Solicited Events” eCRF page), and atrial fibrillation at baseline (“Ongoing” is marked “Yes”). P-values will have a descriptive meaning and any warnings of heterogeneity will be evaluated considering the clinical relevance of the involved variables. The p-values will not be considered to define any formal basis for determining factors to be included in statistical models. If an imbalance of treatment groups with respect to some variables does occur, supplemental analyses with addition of these variables in model may be performed to assess the potential impact on efficacy as appropriate.

For continuous variables, homogeneity of data will be tested by means of t-test.

For categorical variables, Chi-square test will be used. Fisher’s exact test will be used in cases where cell frequencies are less than 5.

Investigational treatment

Study treatment administration will be summarized for the FAS and the Safety set, for patients in the serelaxin arm only. Continuous variables (e.g., dose prescribed in mg, total volume administered in mL, rate of infusion in mL/hr, and duration of infusion in hours/days) will be summarized with standard summary statistics. Categorical variables (e.g., reason for dose change) will be summarized with the number and percentage of patients. Percentages will be computed using the number of patients with non-missing information as denominators, unless otherwise specified.

The analysis of study treatment will be performed for the FAS and Safety set, and will include the following variables:

- Time from presentation to randomization (hours) for both treatment groups. The date of presentation at screening is obtained from the “Index heart failure hospitalization” eCRF page. Time will be presented as elapsed hours and minutes and will be derived as difference + 1 minute. Analysis will be presented also by setting of presentation (Outpatient clinic or office/ Ambulance or Emergency Medical Service/ Emergency Department/ Intensive Care Unit/ Coronary or Cardiac Care Unit/ Cardiology ward/ General ward/ Other).

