- Time from first IV loop diuretic administered for the treatment of the Index Heart Failure event to randomization (hours) for both treatment groups. The first IV loop diuretic administered for index heart failure is obtained from the start date and time of the IV loop diuretic recorded at screening on the “Index heart failure hospitalization” eCRF page. Time will be presented as elapsed hours and minutes and will be derived as difference + 1 minute.
- Study treatment administered (yes/no) for the serelaxin arm only: variable “Any dosage to report?” in the eCRF page “Dosage administration record” and reason why study treatment was not administered: variable “Subject Status” in the eCRF page “Treatment Completion” for patients with no dosage reported.

	<h2 style="margin: 0;">Statistical Analysis Plan</h2>
	
Sponsor: NOVARTIS
 
Protocol number: CRLX030A3301

- Time from presentation to study treatment administration for patients with at least one reported dosage (hours) in the serelaxin arm only. Date of presentation recorded is the earliest of (1) time of presentation either at the ER, ICU/CCU or ward (excludes EMS or other pre-hospital care); or (2) time of first IV loop diuretic prior to arrival at the hospital (this includes in the clinic, ambulance, or any other setting) for the treatment of the current acute heart failure episode. The date of presentation at screening is obtained from the “Index heart failure hospitalization” eCRF page. The date of study treatment administration for patients with at least one reported dosage is obtained from the start date and time of study treatment with a non-missing prescribed dose recorded on the “Dosage administration record” eCRF page. Time will be presented as elapsed hours and minutes and will be derived as difference + 1 minute. Analysis will be presented also by setting of presentation (Outpatient clinic or office/ Ambulance or Emergency Medical Service/ Emergency Department/ Intensive Care Unit/ Coronary or Cardiac Care Unit/ Cardiology ward/ General ward/ Other).
- Time from randomization to study treatment administration (hours) for patients in the serelaxin arm only. The date of study treatment administration is obtained from the start date and time of study treatment with a non-missing prescribed dose recorded on the “Dosage administration record” eCRF page. Time will be presented as elapsed hours and minutes and will be derived as difference + 1 minute.

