Renal deterioration will be assessed as the proportion of patients with an increase of ≥ 0.3 mg/dL from screening in serum creatinine levels. Absolute frequencies and proportions of patients with renal deterioration at each assessment time point in each treatment group will be provided, together with standard errors, asymptotic (Wald) and exact (Clopper-Pearson) confidence limits. Rate of renal deterioration in the two groups will be compared by means of Chi square test at each assessment time point. In case of cell frequencies less than 5, Fisher's Exact test will be used.

Index length of hospital stay

Index length of hospital stay (in hours) will be defined as the index hospitalization discharge date and time (obtained from the "Index hospitalization summary" eCRF page) minus the index hospitalization admission date and time plus 1 minute (obtained from the "hospitalization" eCRF page); it will be presented as elapsed hours.

Subjects still in the hospital at Day 30 will be censored at Day 30. Subjects who die during the initial hospitalization will be assigned the maximum length of stay (including those censored at Day 30) plus 24 hours.

Treatment groups will be compared using a Wilcoxon rank-sum test. Descriptive statistics by treatment group will be presented. Analysis will be done overall and by location for patients presented to Outpatient clinic or office / Ambulance or Emergency Medical Service / Emergency Department / Intensive Care Unit / Coronary or Cardiac Care Unit / Cardiology Ward / General Ward / Other, as recorded on the "Index heart failure hospitalization" eCRF page.

Statistical Analysis Plan

Sponsor: NOVARTIS

Protocol number: CRLX030A3301

Estimated duration (days) of stay in acute care unit (Coronary or cardiac critical care unit / General intensive care unit / Step down unit or telemetry unit / Cardiology department or cardiac ward / General ward), as recorded on the “Index hospitalization summary” eCRF page, will be summarized by treatment group.

Death through Day 30

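### SAP 5.2 tests total index stay by where patients presented; days in ICU, CCU and cardiology, the natural reading of the secondary objective, are only summarized by arm

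*SAP*

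**What the plan says.** Protocol 2.2, repeated in SAP 1.2, sets as a secondary objective the effect of serelaxin "in modifying the index length of stay (LOS) by location (e.g., ICU, CCU, cardiology department) in days and hours (ICU"). The protocol synopsis words it almost identically: "in modifying the index length of hospital stay (LOS) by location (e.g., ICU, CCU, cardiology department) in days (and hours for ICU").

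The data analysis part of the synopsis plans a Wilcoxon rank-sum comparison of index stay, overall and by location. Protocol 9.5.1 names the same test and adds: "Analysis will be done overall and by location (e.g. ICU, CCU, cardiology department"). The only variable it defines is total stay, discharge minus admission. Protocol 6.4.3 gives other examples of location: "Changes in index length of hospital stay and per location (emergency ward, emergency care unit, etc.) will be evaluated by treatment group".

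SAP 5.2 keeps total stay as the tested variable and keeps the Wilcoxon test. It then specifies: "Analysis will be done overall and by location for patients presented to Outpatient clinic or office / Ambulance or Emergency Medical Service", continuing through the emergency department, ICU, coronary or cardiac care unit, cardiology ward, general ward and other. The source is the Index heart failure hospitalization eCRF page. The next paragraph takes estimated days in five acute care units from a different page, the Index hospitalization summary, and says that they will be summarized by treatment group. The resource utilization part of SAP 5.2 repeats that summary and lists the descriptive statistics.

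**The concern.** The word location carries two meanings. In the objective it most naturally means the unit in which the patient spent time. In the SAP's tested analysis it means the setting in which the patient presented.

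A programmer following SAP 5.2 would produce p-values for total stay within presentation subgroups, and tables without a comparison for time in ICU, CCU and cardiology. The between-arm comparison for a stated secondary efficacy objective would then not be made. A results row labelled Intensive Care Unit would hold the whole hospital stay of patients who presented there, and could be taken for ICU duration.

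**Working it through.** No figure in the plan needs to be reproduced. The check compares texts and counts list entries.

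**Step 1: what the eight-item list is.** SAP 5.1 uses the same eight categories when it describes time from presentation to randomization, and takes presentation data from the same eCRF page. There it writes: "Analysis will be presented also by setting of presentation (Outpatient clinic or office/ Ambulance or Emergency Medical Service", followed by the rest of the list. The by-location split in SAP 5.2 is therefore a subgroup by point of entry.

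**Step 2: counts from SAP 5.2.**

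- Presentation settings in which total stay is tested: outpatient clinic, ambulance, emergency department, ICU, coronary or cardiac care unit, cardiology ward, general ward, other = 8.
- Acute care units with recorded days: coronary or cardiac critical care, general ICU, step-down or telemetry, cardiology, general ward = 5.
- Units with a named between-arm test on days in the unit: 0 of 5. This includes the three that the objective gives as examples.
- Units with a like-named presentation setting: coronary or cardiac, ICU, cardiology, general ward = 4 of 5. In those four rows the label suggests unit time but the content is total stay. Step-down or telemetry has no counterpart.
- Settings that lie before hospital arrival: 2 of 8. SAP 5.1 defines presentation as possibly the "time of first IV loop diuretic prior to arrival at the hospital (this includes in the clinic, ambulance, or any other setting"). No inpatient time can accrue in a clinic or an ambulance.

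**Step 3: which meaning fits the objective.** Three points favour time in the unit. The objective asks for ICU stay in hours, which is natural for time spent there and odd for the total stay of patients who happened to enter through the ICU. The examples in Protocol 2.2 and 9.5.1 are inpatient units. Protocol 3.6 motivates the trial partly by earlier reductions in "length of stay during the index hospitalization, including duration of intensive care". That passage describes earlier studies and does not define this trial's variable, so it supports the reading without settling it.

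**Step 4: how far the two analyses can diverge.** Two hypothetical patients show it.

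- Patient A presents to the emergency department, then spends 2 days in ICU and 6 on a ward. The tested analysis records 2 + 6 = 8 days under Emergency Department and nothing under ICU.
- Patient B presents in the ICU, spends 1 day there and 7 on a ward. The tested analysis records 1 + 7 = 8 days under Intensive Care Unit.

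On days in ICU the values are 2 and 1. In the tested ICU row they are absent and 8.

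**Step 5: whether another passage cures it.** SAP 5.1 says in general terms that the data will be analysed according to Section 9 of the protocol. SAP 5.2 then gives a specific and different rule for this endpoint, and the specific rule is the one that would be programmed. Protocol 9.5.3 plans only summary statistics for unit stay, but as resource utilization. It does not cancel the comparison by location in the synopsis and in 9.5.1.

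**The case against.** The best reply is that the SAP largely follows what the protocol defines. Protocol 9.5.1 has one variable, total stay. SAP 4.1 speaks of admission-to-discharge stay evaluated by location, which a split of total stay satisfies literally. Time in specific care units appears in so many words only under resource utilization, where summary statistics are all that is planned. Those summaries will be reported, so unit stay will not be missing from the results. The endpoint is also one of several secondary ones without multiplicity control.

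Much of this stands. Time in the unit is an inference, though a strong one, and the protocol shares responsibility. What the reply does not explain is the request for ICU hours, or how a test by clinic or ambulance of presentation answers a question about ICU, CCU and cardiology.

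A reader might infer three further things that the documents do not support.

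- That the location lists contradict each other. They are open examples, introduced by e.g. or closed by etc., and different examples are not a conflict.
- That unit days are singled out by having no interval. Overall stay also gets only a rank-sum test and descriptive statistics.
- That scoring survivors never in a unit as 0 makes the result independent of unit entry. It does not, because a survivor's value depends on whether the unit was entered. It only avoids restricting the comparison to those who entered.

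**Conclusion.** The point holds as a mismatch between objective and analysis. The tested by-location analysis in SAP 5.2 covers total stay in 8 presentation settings, and 0 of the 5 unit-duration variables have a named comparison. This rests on reading the objective as time in the unit, which is the better reading but is not spelled out as a variable anywhere in the protocol.

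The consequence is limited to one secondary objective, and descriptive unit days will still be shown. The documents give no ICU use, no distribution of stay and no expected effect on it, so nothing can be said about power. It should be corrected before database lock, because the change is small and the present row labels invite misreading.

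**What to change.** An SAP edit is enough. Changing the protocol text would need a formal amendment under Protocol 11.1 and is not required.

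1. In SAP 5.2, make days in each acute care unit the by-location variable, at least for ICU, CCU and cardiology. Compare arms on the FAS with the protocol's Wilcoxon rank-sum test. Use the unit days already on the Index hospitalization summary page, summed across assessments as the resource utilization text describes. Include all patients, count survivors never in a unit as 0 days, and count days up to Day 30 for patients still in hospital.
2. State before database lock how in-hospital deaths are scored for unit days. The existing rule, maximum stay plus 24 hours, is written for total stay. Extending it to each unit is one option, but it gives every unit's test the same death component, and more days on a general ward are not clearly worse. Observed days are the other option. Choose one and run the other as a sensitivity analysis.
3. Label the presentation-setting results as subgroups of total stay, not as stay by location.
4. Report ICU stay in hours if the eCRF collects it, which the documents do not show. Otherwise say in the SAP that days are used.

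The cost is SAP wording, a few tables and three to five more secondary tests at the unadjusted two-sided 0.05 level, plus the sensitivity runs. No new data are needed for unit days, and the primary and overall-stay analyses are unchanged.
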